### **9.3.2 Exclusion Criteria**

The presence of any of the following excludes a patient from study enrollment:

1. Patient has current or previous evidence of muscle invasive (muscularis propria) or metastatic bladder cancer disease
2. Patient has received prior investigational therapy for NMIBC
3. Patient has received any therapy for NMIBC within 10 weeks before the start of study treatment other than surgical resection, 1 dose of chemotherapy, and previous BCG
4. Patient is intolerant to previous BCG treatment in the absence of meeting other criteria for BCG unresponsiveness and adequate BCG therapy
5. Patient has received external beam radiation therapy for bladder cancer at any time or for any other condition
6. Patient has an active infection, including urinary tract infection (viral, bacterial, or fungal) and cystitis
7. Patient has urinary tract signs or symptoms that preclude retention of drug in the bladder; this does not include anticholinergic drugs
8. Patient is known to have tested positive for human immunodeficiency virus (HIV). No HIV testing is required if patient is not known to have tested positive

9. Patient is female and is pregnant or breastfeeding
10. Patient has any medical, psychological, or social condition or situation that may, in the investigator's opinion, make it difficult for the patient to tolerate study medication or comply with study procedures and other requirements. This includes but is not limited to active infections, poorly controlled diabetes, uncontrolled cardiac arrhythmia, angina pectoris, or hypertension
11. Patient has a known presence or history of malignancy of other organ system within the 5 years before study start, with the exception of non-melanoma skin cancer (eg, basal cell carcinoma or squamous cell carcinoma of the skin); very low or low-risk prostate cancer (by National Comprehensive Cancer Network guidelines) defined as prostate-specific antigen <10 ng/dL, Gleason score ≤6, and clinical stage T1c; or patients who have been disease-free for at least 2 years following stage 1 or 2 cancer
12. Patient is on immunosuppressive therapy or has had a transplant within 12 months before study start, except for chronic use of corticosteroids (eg, rheumatoid arthritis, asthma, chronic obstructive pulmonary disease, or any other similarly chronic use of steroids)
13. Patient has any other significant disease that, in the opinion of the investigator, would prevent study entry

## **9.4 Study Treatment Plan**

### **9.4.1 Enrollment Period**

At study entry, patients with BCG-unresponsive disease can have completely resected papillary disease, resected papillary disease with CIS, or CIS alone. It is required that the first 35 patients treated have CIS (with or without papillary disease).

To fully define the extent of disease at study entry, eligible patients must have had a recent TUR (within 6 weeks/42 days) prior to start of treatment. No more than 42 days may elapse between complete resection of papillary disease and start of therapy. Patients with T1 disease should undergo resection at the base of the lesion to ensure the absence of muscle-invasive disease. Patients for whom the last TUR was performed by a study investigator (or an on-site designee) ≤42 days before the first study treatment are not required to have a re-TUR. It is recommended that patients who had a TUR performed elsewhere and/or patients with high-grade disease at baseline (high-grade Ta, high-grade T1, or Tis) have a re-TUR performed ≤42 days before the first study treatment to exclude any visibly growing stage Ta or T1 papillary tumors (in which case, re-TUR is indicated), remaining CIS lesions, and/or exclude T2 (muscle-invasive) disease. Any visible CIS lesions should be fulgurated at that time as needed.

Patients should be staged before enrollment. Staging should include the use of bladder mapping and random biopsies in patients with CIS or high-grade papillary disease ([Gudjonsson et al. 2012](#)). In this study, tumor staging will be conducted in accordance with the AUA-adopted TNM staging classification ([Sobin et al. 2009](#)), and grading will follow the World Health Organization (WHO) grading classification (2004 revision, Miyamoto et al. 2010) with tumors categorized as papillary urothelial neoplasm of low malignant potential, low-grade, or high-grade. TNM classifications are shown in [Table 9.1](#).

Urine cytology results should also be obtained and evaluated prior to enrollment.

**Table 9.1. TNM Staging Classifications**

T - Primary Tumor	N – Lymph Nodes	M - Distant Metastasis
Ta: Noninvasive papillary carcinoma	Nx: Regional lymph nodes cannot be assessed	M0: No distant metastasis
Tis: Carcinoma in situ	N0: No regional lymph node metastases	M1: Distant metastasis
T1: Tumor invades sub-epithelial connective tissue	N1: Metastasis in a single lymph node in the true pelvis (hypogastric, obturator, external iliac, or presacral)	
T2: Tumor invades muscularis 
 
• T2a: Superficial muscle (inner half)
 
• T2b: Deep muscle (outer half)
 
	N2: Metastasis in multiple lymph nodes in the true pelvis	
T3: Tumor invades peri-vesical tissue (beyond muscularis) 
 
• T3a: Microscopically
 
• T3b: Macroscopically (extravesical mass)
 
	N3: Metastasis in a common iliac lymph node	
T4: Tumor invades any of the following: prostate, uterus, vagina, pelvic wall, abdominal wall 
 
• T4a: Prostate, uterus, vagina
 
• T4b: Pelvic wall, abdominal wall
 
		

Source: [Sobin et al. 2009](#).

### ***Administration of BC-819 During Treatment Sessions***

During treatment sessions, patients are encouraged to minimize fluid intake for 6 hours before instillation of the study medication and for 2 hours thereafter or until voiding, whichever comes first.

At each treatment session, a thin, sterile tube (called a Foley catheter) will be inserted into the bladder to drain urine and serve as a port of entry for the planned bladder instillations. Size 12-Fr (1 "French" or "Fr" = 0.33 mm = .013") catheters are normally suggested, but use of other sizes is acceptable per the investigator's discretion. Should the patient have an enlarged prostate (eg, benign prostatic hyperplasia) or any other condition that may obstruct the urethra, a Coudé-tipped catheter (called a Tiemann catheter) angled upward at the tip may be used to assist in negotiating the upward bend in the male urethra in order to completely drain the bladder. Size 10-Fr catheters are normally suggested for this scenario, but use of other sizes is acceptable. A 20-mg dose of BC-819 in a total volume of 50 mL will then be instilled into the bladder over approximately 4 minutes. After infusion, a further saline/sterile water flush may be needed to ensure that the BC-819 sitting in the catheter tubing is also flushed into the bladder space ensuring that full dose is delivered. The drug should be retained in the bladder for as long as possible (for a maximum of 2 hours but not less than 30 minutes) to allow for good topical contact between the drug and the inner bladder epithelium, which results in improved penetration (also referred to as plasmid transfection) of the drug into the cells through 1 or more bladder inner wall layers. The time that the instillation is completed and the time of postdose voiding should be recorded in the source documents.

#### **9.4.2 Induction Phase**

Study treatment will start within 7 days of enrollment and  $\leq$ 42 days from the last TUR or biopsy. Initial therapy begins with a 10-week induction phase. Patients will receive an intravesical installation of BC-819 20 mg/50 mL once per week for 10 weeks during this phase.

#### **9.4.3 Maintenance Treatment**

Upon completion of the induction phase, patients will transition to a maintenance therapy schedule of BC-819 (ie, once every 3 weeks). The first maintenance treatment and visit will occur 12 weeks after enrollment (Visit 11). Treatments will continue every 3 weeks for 84 additional weeks until the end of the study (end of study [EOS] Visit 39) at 96 weeks.

Patients who have recurred with high-grade papillary carcinoma or with metastatic disease will be considered treatment failures and will be withdrawn from the study. All suspected recurrences (by direct visualization) must be documented by biopsy results.

Patients who are free of high-grade tumors or who are tumor-free (ie, patients benefiting from treatment) will be allowed to continue to receive maintenance therapy every 3 weeks per the schedule of treatment during the maintenance phase ([Table 12.2](#) and [Table 12.3](#)) as long as response status is maintained and they are not considered a treatment failure.

Patients will undergo repeat direct visualization (ie, cystoscopy  $\pm$  biopsy and cytology) and re-TUR (as needed for cause) every 12 weeks during the first and second year of the study.

All enrolled patients will complete the following quality of life questionnaires at the visits indicated in the study schedule ([Table 12.1](#) and [Table 12.2](#)):

- The European Organization for Research and Treatment of Cancer quality of life Questionnaire (EORTC QLQ-C30; a general questionnaire for cancer)
- Quality of Life Questionnaire–Non-Muscle-Invasive Bladder Cancer Questionnaire (QLQ-NMIBC24; a specific questionnaire for NMIBC disease)

The end of the study will be the 96-week visit (Visit 39) for all patients.

#### **Maintenance Treatment and Repeat Direct Visualization Schedule**

Patients benefiting from treatment with no documented progression or high-grade recurrence will continue to receive maintenance therapy every 3 weeks starting from Visit 11 (Week 12) onward.

During the first-year maintenance treatment, patients will continue treatment with BC-819 every 3 weeks as listed below:

- Visit 11 or 12 weeks (3 months)
- Visit 12 or 15 weeks
- Visit 13 or 18 weeks
- Visit 14 or 21 weeks
- Visit 15 or 24 weeks (6 months)
- Visit 16 or 27 weeks
- Visit 17 or 30 weeks
- Visit 18 or 33 weeks
- Visit 19 or 36 weeks
- Visit 20 or 39 weeks
- Visit 21 or 42 weeks
- Visit 22 or 45 weeks
- Visit 23 or 48 weeks (12 months)

As mentioned above, urine cytology, cystoscopy, and re-TUR (as needed for cause) will be performed every 12 weeks (within 2 weeks prior to the maintenance treatment) during the first year of the study (in alignment with the AUA standard of care) and are required before the maintenance treatment at the following visits:

- Visit 11 or 12 weeks (3 months)
- Visit 15 or 24 weeks (6 months)
- Visit 19 or 36 weeks
- Visit 23 or 48 weeks (12 months)

The 12-week visit (Visit 11) will include the initial evaluation of the primary endpoint of complete response rate in CIS patients.

During the second year of maintenance treatment, patients will continue treatment with BC-819 every 3 weeks as listed below:

- Visit 24 or 51 weeks
- Visit 25 or 54 weeks
- Visit 26 or 57 weeks
- Visit 27 or 60 weeks
- Visit 28 or 63 weeks
- Visit 29 or 66 weeks
- Visit 30 or 69 weeks
- Visit 31 or 72 weeks (18 months)
- Visit 32 or 75 weeks
- Visit 33 or 78 weeks
- Visit 34 or 81 weeks
- Visit 35 or 84 weeks
- Visit 36 or 87 weeks
- Visit 37 or 90 weeks
- Visit 38 or 93 weeks
- Visit 39 or 96 weeks (24 months) – end of study assessments with no treatment

Mandatory second year cystoscopy should be performed within 2 weeks prior to the following visits and is required before the maintenance treatment:

- Visit 27 or 60 weeks
- Visit 31 or 72 weeks (18 months)
- Visit 35 or 84 weeks
- Visit 39 or 96 weeks (24 months)

## 9.5 Dosing Delays

All toxicity in this study will be graded in accordance with CTCAE guidelines (version 5.0).

- No dose reduction of BC-819 is planned
- No dose adjustments are allowed
- A delay of up to 2 weeks from the scheduled treatment ( $\leq 2$  weeks) is allowed at the investigator's discretion
- Administration of any missed doses should be discussed with and approved by the sponsor medical monitor or delegate
- Skipped doses or termination of treatment will be based on the observed toxicities (as specified below)

Grade 3 to 4 BC-819 related or unrelated AEs should be managed as follows:

- First occurrence of Grade 3 or 4 toxicity—withhold treatment until toxicity has improved to Grade  $\leq 1$
- Second occurrence:

- Of Grade 3 toxicity— withhold treatment until toxicity has improved to Grade  $\leq$  1
- Of Grade 4 toxicity— permanently discontinue treatment
- Third occurrence of Grade 3 toxicity— permanently discontinue treatment

Types of AEs that would warrant withholding treatment include but are not necessarily limited to persistent irritative symptoms lasting  $>48$  hours, fever  $>100^{\circ}\text{F}$  ( $37.8^{\circ}\text{C}$ ), sepsis, and hematuria. Patients should be reassessed at 1-week intervals until the applicable AE has resolved, up to a maximum delay of 5 weeks.

During the induction phase, the investigator may skip only 1 scheduled induction treatment because of a toxicity-related delay without disqualifying the patient from the study and warranting study withdrawal. All enrolled patients must receive a minimum of 5 of the planned 6 induction phase BC-819 instillations. Patients requiring more than 1 scheduled induction treatment to be skipped will require sponsor medical monitor or delegate approval to continue study participation. During the maintenance phase of the study, investigators may withhold treatment because of Grade 3 or 4 toxicity for 1 visit only.

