### 7.3.2 Phase 2 Monotherapy Study

Following the Phase 1 study, a Phase 2 study of BC-819 was completed in patients with superficial bladder cancer of intermediate risk. The primary endpoint in this study was to determine tumor recurrence in resected patients; a secondary endpoint was response rate of marker lesions. Patients with histologically confirmed superficial bladder cancer with recurrent stage Ta (any grade) or T1 (low-grade) NMIBC were eligible to enter the study. Patients with CIS lesions were excluded. All tumor specimens resected at baseline were H19 positive. Patients must have failed at least 1 prior conventional therapy including either BCG or chemotherapy and, as in the Phase 1 study, have 1 tumor  $\leq$ 1.0 cm in diameter to serve as a “marker” tumor after removal of all other tumors. Treatment in this study was composed of an initial induction phase of 6 weekly 20-mg instillations followed by safety and efficacy assessment at Week 9. Subsequently, in the absence of recurrence or toxicity requiring discontinuation of therapy, these patients continued to receive maintenance therapy of 3 weekly courses every 12 weeks.

A total of 47 patients were treated in this study; 38 patients (81%) received prior BCG, and more than half of the patients received other therapies as well (45% of patients received 2 or more prior treatments). Eight patients were not evaluable due to protocol violations and early withdrawal.

At the time of primary assessment at Week 9 after the start of treatment, 13 patients (28% of the intent-to-treat [ITT] population and 33% of the per-protocol population) had complete disappearance of the marker lesion, and no new lesions were reported. Twenty-six patients (55%) in the ITT population and 64% of patients in the per-protocol population had no new lesions at 3 months (the primary endpoint). Median time to recurrence for both the ITT and per-protocol populations was 11.3 months; 46% and 36% of patients were free of recurrence at 12 and 18 months, respectively, and 33% remained recurrence-free at 24 months follow-up. Treatment was very well tolerated. No patients discontinued because of treatment-related adverse events (TEAEs).

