## 12. STUDY PROCEDURES AND FLOWCHARTS

The administration of BC-819 is separated into 2 phases, the induction phase and the maintenance phase.

During the induction phase, eligible patients will receive BC-819 once per week for 10 consecutive weeks. The flow chart for the induction phase is [Table 12.1](#).

During the maintenance phase, patients will transition to once every 3 weeks administration of BC-819 and will be evaluated every 12 weeks by cystoscopy for staging of response in order to determine continued participation. The urine cytology and cystoscopy must be completed within 14 days prior to the next administration of BC-819 and fully evaluated before initiating the treatment. The flow charts for the maintenance phase are [Table 12.2](#) and [Table 12.3](#).

In each of the the study flow charts, a study week is defined as 7 days. A description of each procedure is in Section [12.1](#). End of study procedures are required within 4 weeks of leaving the study.

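### Protocol 9.5 sets the induction minimum at 5 of 6 instillations, but induction has 10 and the adjacent one-skip limit implies 9; it also does not say whether a delayed dose is made up or skipped

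*Protocol*

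**What the plan says.** The length of induction is given consistently. Protocol 9.4.2: "Patients will receive an intravesical installation of BC-819 20 mg/50 mL once per week for 10 weeks during this phase". Protocol Section 12 says "eligible patients will receive BC-819 once per week for 10 consecutive weeks". The synopsis, Section 9.1, Table 12.1 (V1 on Day 1 to V10 on Day 64), SAP 3.1 and SAP Section 4 agree.

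Section 9.5 is the exception. Its last paragraph contains three rules:

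- **Skip limit:** "the investigator may skip only 1 scheduled induction treatment because of a toxicity-related delay without disqualifying the patient from the study".
- **Floor:** "All enrolled patients must receive a minimum of 5 of the planned 6 induction phase BC-819 instillations".
- **Beyond one skip:** continuation needs approval from the sponsor medical monitor or delegate.

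Earlier in 9.5, the investigator may delay a dose by up to 2 weeks at discretion. For toxicity: "Patients should be reassessed at 1-week intervals until the applicable AE has resolved, up to a maximum delay of 5 weeks". On missed doses: "Administration of any missed doses should be discussed with and approved by the sponsor medical monitor or delegate".

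Visit 11 is at Week 12 (Day 84 in Table 12.2) and holds the first evaluation of the primary endpoint (9.4.3). Cystoscopy and cytology are due in the preceding 14 days. Under 9.6, CIS not cleared by Week 12 means discontinuation and non-response in the primary analysis.

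**The concern.** The floor is a mandatory participation rule that stands beside withdrawal language, and its denominator belongs to a course that this trial does not give. Two sentences of one paragraph then point to different minimums. The person most exposed is the medical monitor, who decides on continuation after a second skip. One sentence suggests that anything below 9 is exceptional; the next, read literally, accepts 5.

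The silence on delayed doses adds to this. Whether a delay uses up the single permitted skip, or only moves the remaining doses later, decides whether the floor is tested at all. It also decides whether dose 10 comes before or after the Visit 11 assessment.

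What is at stake is consistent handling of patients. A treated CIS patient who is withdrawn before Week 12 stays in the full analysis set denominator without a documented response.

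**Working it through.** **1. The stated figure.** One skip from a 6-dose course gives 6 − 1 = 5, so the sentence agrees with the skip limit only if induction has 6 doses. Induction has 10, and the same subtraction gives 10 − 1 = 9. The literal floor is 5/10 = 50% of the course; the skip limit implies 9/10 = 90%.

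**2. Delayed doses made up at weekly spacing.** Dose *j* is due on Day 1 + 7(*j* − 1), so dose 10 is due on Day 64. A delay of *L* days moves it to Day 64 + *L*.

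| Delay | Dose 10 | Relative to Day 84 |
|---|---|---|
| 2 weeks | Day 78 | 6 days before |
| 3 weeks | Day 85 | 1 day after |
| 4 weeks | Day 92 | 8 days after |
| 5 weeks | Day 99 | 15 days after |

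The 2-week discretionary delay therefore still fits before Visit 11.

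**3. Made up as fast as allowed.** Section 12.1 forbids doses closer than 5 days apart. If dose *k* is delayed by *L* days and the rest follow every 5 days, dose 10 falls on Day (7*k* − 6) + *L* + 5(10 − *k*) = 44 + 2*k* + *L*. This passes Day 84 when *L* > 40 − 2*k*:

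- *k* = 2: more than 36 days, so never within the 35-day limit
- *k* = 5: more than 30 days
- *k* = 8: more than 24 days
- *k* = 10: more than 20 days

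For a 35-day delay, dose 10 falls on Day 83 if the delay is at dose 2, Day 85 at dose 3 and Day 99 at dose 10. Catch-up recovers only part of a late delay.

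**4. Delayed doses counted as skipped (calendar unchanged).** A 14-day delay at any of doses 2 to 9 loses 2 doses and leaves 8 of 10. The investigator's own discretionary delay would then exceed the one-skip limit and need approval. A 35-day delay at doses 2 to 6 loses 5 and leaves 5 of 10, which meets the literal floor while being four skips beyond the limit.

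**5. How often the floor could matter.** The documents give no skip rate. As an assumption, let each of 10 doses be skipped independently with probability *q*. Then P(2 or more skips) = 1 − (1 − *q*)^10 − 10*q*(1 − *q*)^9, which is 0.0162 at *q* = 0.02 and 0.0861 at *q* = 0.05. Among 70 to 100 CIS patients that is 1.1 to 1.6 or 6.0 to 8.6 patients. Fewer than 5 doses has probability below 0.00001 at both rates. Toxicity holds cluster within patients, so these figures are only a guide.

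**The case against.** The best reply is that the wrong number does little harm, because the sentences around it already govern conduct: one skip, then monitor approval. Much of this stands. No site can stop at 5 doses on its own authority, and a patient with 9 of 10 satisfies both sentences, so the paragraph can be followed in the ordinary case. What remains is that the approval step has two incompatible numbers beside it.

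Several stronger readings are tempting but not supported.

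- **That the 5-week limit was written for a 6-dose course.** On 6 weekly doses a 35-day delay would end on Day 36 + 35 = Day 71, which fits, and the earlier monotherapy study did use "Treatment in this study was composed of an initial induction phase of 6 weekly 20-mg instillations". But the sentence is not confined to induction. It also covers 3-weekly maintenance, and the documents do not say where the limit, or the figure 6, came from.
- **That there is no rule for the Week 12 assessment.** There is one: Visit 11 is a fixed landmark with a mandatory CIS response assessment. SAP 7.1.2 tabulates by recorded visit even when out of window, and the primary endpoint accepts a response documented after Week 12. The gap concerns doses, not the assessment date.
- **That the per-protocol set is left without a dose criterion.** Protocol 13.2 and SAP Section 6 say that classes of major deviation will be defined before the primary analysis, which itself uses the full analysis set.

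The ±1 week maintenance window in 12.1 could also move Visit 11 to about Day 91 and absorb a 3-week delay (Day 85). It does not absorb 4 or 5 weeks at weekly spacing (Days 92 and 99).

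**Conclusion.** The point holds as an error in an operative rule. The induction floor in 9.5 is stated for 6 doses and should be stated for 10. The gap between the literal reading and the adjacent skip limit is 5 against 9 doses. This rests on the documents alone.

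The linked omission is also real. Section 9.5 does not say whether a delayed induction dose is made up or skipped, and at weekly spacing a toxicity delay of 3 weeks or more puts dose 10 on Day 85 to 99, after the Day 84 assessment. Such delays are possible rather than routine, and making up missed doses already needs the monitor's approval.

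A reader might infer a bias in the complete response rate or a loss of power. Neither is claimed: the documents give no skip or delay rate, and assessing a patient before induction ends could only lower the response rate. Correct it at the next amendment.

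**What to change.** In the last paragraph of Protocol 9.5:

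1. Replace the floor sentence with: *Patients must receive at least 9 of the planned 10 induction instillations unless the medical monitor or delegate approves continuation after more than 1 skipped dose.* This agrees with the skip limit and with the approval sentence that stays. If the sponsor also wants an absolute floor below which approval is not possible, give it as a number out of 10.
2. Add one sentence saying whether a delayed induction dose is made up (never closer than 5 days to another dose) or counted as skipped.

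Keep the Week 12 assessment at Visit 11 for all patients, whatever the delay. Letting the sponsor's monitor set later dates case by case would give selected patients in an open-label, single-arm trial more time to respond, and would delay detection of persistent CIS.

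The cost is two sentences in one amendment, with no added patients or procedures. The SAP does not repeat the wrong floor and needs no change. The price of the fixed landmark is that a few patients with long delays may be assessed before their last induction dose, which is the conservative choice.
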